## PROTOCOL SYNOPSIS

Title	CONTINUED ACCESS PROTOCOL: Demonstration of the Safety and Effectiveness of ReCell® combined with Meshed Skin Graft for Reduction of Donor Area in the Treatment of Acute Burn Injuries
Purpose	The overall purpose of this is study to provide continued access to the ReCell device following completion of protocol CTP001-6, and to allow for collection of supplementary clinical outcome data for the ReCell device when used as an adjunct to meshed grafts in subjects with acute thermal burn injuries requiring skin grafting for closure of burn injuries
Design	
This is a prospective, randomized, multicenter, evaluator blinded, within-subject controlled study. Patients 5 years or older with a total body surface area (TBSA) thermal burn injury between 5 and 50% (inclusive) will be considered for participation in this study. Following burn excision and confirmation of eligibility, a grafting plan will be developed and documented in accordance with investigators' standard of care. Among the excision sites, two comparable contiguous or non-contiguous areas (i.e., similar in burn injury depth, graft plan and size) at least 300 cm^2 in size will be identified and labeled as Area A and Area B. The wound regions will be randomly assigned to receive grafting consistent with the Investigator's pre-identified graft plan (control) or to receive application of the ReCell- generated cell suspension applied over a graft more widely meshed than identified in the pre-specified graft plan (ReCell-treated). For example, if the graft plan called for a 2:1 mesh graft, for the ReCell-treated wounds, the area will be treated with 3:1 mesh graft and over-sprayed with the ReCell-generated cell suspension. The donor area for skin allocated to ReCell and control treatment areas will be measured and documented. The two treatment areas will be compared with respect to healing characteristics and the amount of donor skin harvesting required.
 
Follow-up visits will be performed at 1, 2, 4, 6, 8, 10, 12, 24, 36 and 52 weeks post treatment. Acute healing and pain outcomes will be evaluated in the early post-operative period (i.e., through 12 weeks). Pain, healing durability and scar outcomes will be evaluated in the longer-term follow-up visits (i.e., 24, 36 and 52 week visits). Treatment-related and serious adverse events will be captured throughout the duration of the study.
 
Treatment-area closure will be evaluated via direct visualization by the treating investigator and by a qualified clinical investigator blinded to treatment allocation (i.e., Blinded Evaluator). The blinded assessment will serve as the primary healing assessment.
 
At all visits, all subjects' study treatment areas will be documented photographically using standardized digital photography. Scar outcomes will be measured using the Patient and Observer Scar Assessment Scale (POSAS) questionnaire which includes components for both the Blinded Evaluator and the patient.

Co-Primary Effectiveness Endpoints	
1. Confirmed treatment area closure at (or prior to) the Week 8 visit. Complete wound closure is defined as skin re-epithelialization without drainage, confirmed at two consecutive study visits at least 2 weeks apart by direct visualization by a qualified clinician. Blinded Evaluator assessment of wound closure will be performed at Weeks 4, 6, 8, 10 and 12.
 
2. The actual expansion ratios (treatment area to donor site area, inclusive of donor skin needed for secondary treatments) will be calculated separately for the ReCell and control treatments.
 
Treatment area and donor area will be based on measurements of the treatment and donor site wound bed at the time of the grafting procedure (obtained intra-operatively). Calculation of expansion ratios will include any donor skin required for re-treatments performed to achieve wound closure, if applicable.

Additional Effectiveness Endpoints	
The following additional effectiveness endpoints will be investigated: Subject Satisfaction at Week 24 (evaluating whether there is a preference for the ReCell treatment), 24 Week Observer POSAS Overall Opinion Score and 24 Week Patient POSAS Overall Opinion Score

Safety	
Safety will be assessed with evaluation of the following:
 
 
1. Delayed healing (all visits)
 
2. Infection (all visits)
 
3. Allergic response to trypsin (all visits)
 
4. Treatment area durability, in terms of any evidence of recurrent wound breakdown following initial complete closure (Week 12, 24, 36 and 52)
 
5. Scars necessitating surgical intervention
 
6. Treatment-area pain via numeric rating scale (1-10, where 1 represents no pain and 10 represents worst possible pain) will be evaluated at all visits, and incorporated as a component of the POSAS beginning at Week 12
 
7. Treatment-related and serious adverse events (all visits)
 

Other Evaluations	
 
1. Healing assessment by treating investigator (all visits)
 
2. POSAS and Subject Satisfaction evaluations at Week 12, 36 and 52
 
3. Subject and Blinded Evaluator blinding effectiveness
 

Enrollment	
Up to 60 patients enrolled at up to 18 investigational sites in the United States

Analysis	
Data will be analyzed and summarized in an interim analysis at a time to coincide with the submission of the ReCell marketing application. At that time all available data will be presented. Data will be analyzed consistent with the statistical plan develop for the CTP001-6 protocol; however, there are no formal statistical hypotheses to be investigated.

Statistical Consideration	
It is anticipated that up to 60 subjects may be accrued in the period between the time the protocol is approved and receipt of FDA marketing approval for the ReCell device. Primary effectiveness will be assessed on the following two analysis sets: Intent to treat population (ITT) – All those enrolled into the study who are randomized; and Per protocol population (PP) – ITT subjects who receive both study treatments and have no major protocol deviations.
 
For the co-primary effectiveness endpoint for confirmed treatment area closure, the hypothesis test of non-inferiority will be one-sided with a 5% significance level; for the endpoint of relative reduction in donor site area, the hypothesis test of superiority will be one-sided with a 2.5% significance level, all other statistical tests will be two-sided at the 5% significance level, unless otherwise noted.
 
Data will be analyzed and summarized in an interim analysis at a time to coincide with the submission of the ReCell marketing application.
 
For evaluation of the co-primary effectiveness endpoints, it is anticipated that there will be minimal missing data. However, multiple imputation and sensitivity analyses (e.g., pattern mixture models) will be performed if appropriate to account for missing data.

----------------------------------	---

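### Non-serious local events outside the named safety items, and donor-site events those items do not clearly cover, are captured only if judged treatment-related

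*Combined protocol and SAP*

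**What the plan says.** The Design row of the Protocol Synopsis gives the capture rule: "Treatment-related and serious adverse events will be captured throughout the duration of the study". Item 7 of the Safety row repeats it: "Treatment-related and serious adverse events (all visits").

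The Safety row has six other items:

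- Item 1: "Delayed healing (all visits")
- Item 2: "Infection (all visits")
- Item 3: "Allergic response to trypsin (all visits")
- Item 4, for the treatment area: "any evidence of recurrent wound breakdown following initial complete closure (Week 12, 24, 36 and 52")
- Item 5: "Scars necessitating surgical intervention"
- Item 6: "Treatment-area pain via numeric rating scale", at all visits

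The Design row has closure judged by the treating investigator and by a Blinded Evaluator, whose assessment is primary. The Blinded Evaluator also contributes to the scar scale. The Other Evaluations row adds a check of how well blinding worked for both subjects and evaluators. Treatment areas are photographed at every visit. Donor area is measured during the operation for the expansion ratio, which is a co-primary endpoint.

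**The concern.** Each patient carries both treatments, so local events are the kind of safety information that can be set side by side within a patient. A systemic event cannot be assigned to one area. For non-serious local events not already covered by a named item, entry to the database depends on a judgement of cause. If the person judging knows which area received ReCell, similar events on the two areas could be attributed differently. One would be recorded and the other would not.

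Donor sites deserve the same attention. Reduced donor area is the benefit in the study title, yet no safety item names the donor site. An event never recorded cannot be restored by analysis: the missing-data provisions in the Statistical Consideration row concern the co-primary endpoints.

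**Working it through.** The plan gives no figure on this point. The check compares the capture rule with each safety item.

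**Reading of the rule.** I read it as covering events that are serious, treatment-related, or both. A non-serious event then enters as an adverse event only if it is judged treatment-related.

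**Item by item (Safety row).**

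| Item | Causality condition | Site stated |
|---|---|---|
| 1 Delayed healing | none | none |
| 2 Infection | none | none |
| 3 Allergic response to trypsin | defined by its cause | none |
| 4 Recurrent breakdown | none | treatment area |
| 5 Scars needing surgery | none | none |
| 6 Pain | none | treatment area |
| 7 Adverse events | treatment-related, unless serious | none |

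Five items (1, 2, 4, 5, 6) carry no causality condition, one (3) is defined by its cause, and one (7) carries the filter: 5 + 1 + 1 = 7.

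**What is left to item 7 alone.**

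- At Area A or B: non-serious events that are not delayed healing, infection, breakdown, scars needing surgery or pain. A local reaction not attributed to trypsin is an example.
- At donor sites: items 4 and 6 are confined to the treatment area, so non-serious donor-site pain is outside item 6. A donor-site scar that needs no surgery is outside item 5. Items 1, 2 and 5 name no site, so they may or may not extend to donor sites. The photographs are specified for the treatment areas only.

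**Who judges.** The Synopsis gives the Blinded Evaluator closure and scar assessment. It assigns the relatedness judgement to nobody. The contrast between the treating investigator and the Blinded Evaluator suggests that the former knows the allocation, but this is an inference.

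**Size.** If N residual events occur on each area and a proportion p is judged related, the recorded count is N × p, and the spurious difference is N × (p1 − p2). The documents give neither N nor p. Purely as an assumption, take N = 10 on each area:

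- Equal attribution: the difference is 0, although events are still lost on both sides whenever p is below 1.
- 60% against 30%: 10 × 0.60 = 6 and 10 × 0.30 = 3, a recorded difference of 3 when the true difference is 0.
- Extremes: 10 against 0, in either direction.

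This shows the mechanism and that its sign is open. It estimates nothing about this trial.

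**The case against.** The strongest objection is that the main local outcomes are already collected whatever their cause. That is correct. A reader might infer from the capture rule that local events in general are filtered before the two areas are compared. The Safety row contradicts this for five of its seven items, and photographs at every visit give a further unfiltered record of visible changes on the treatment areas.

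Four more objections have force:

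- A reader might infer that only the evaluator is blinded and that an unblinded team decides relatedness. The documents do not support this: subject blinding is also assessed, and the person who decides relatedness is not named.
- A reader might take treatment-related to mean device-related. The text does not limit it so. If it covers the control graft and donor harvest too, more events would be captured and the asymmetry would shrink.
- The between-area comparison named in the Design row is of healing and donor skin harvested. No area-to-area comparison of adverse events is described, so this is not the trial's main safety contrast.
- This is a continued-access study that, according to the Analysis row, has no formal hypotheses and is to be analysed consistently with CTP001-6. A different capture rule could disturb that consistency.

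These objections narrow the point without removing it. The wider meaning of treatment-related still requires a judgement of cause. The study's stated purpose includes supplementary clinical outcome data, so descriptive counts are part of its product. The consistency concern is met by keeping a related-only table. Only synopsis text is available, and fuller definitions may stand elsewhere, but the point rests on a rule stated twice and not on a missing definition.

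**Conclusion.** The point holds in a narrow form. Non-serious local events outside Safety items 1 to 6, and non-serious donor-site events those items do not clearly cover, are recorded only after a judgement of cause that the text does not say is blinded. Counts of these residual events by area and donor site may be incomplete or differentially recorded, in either direction.

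The size cannot be derived, and the 6 against 3 illustration must not be read as an estimate. The documents do not show that any bias has occurred or that the main local safety outcomes are affected. The conclusion assumes that the capture rule operates as written and that no fuller adverse event section widens it. It is a cheap improvement of low severity.

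**What to change.** Change the capture rule to three classes:

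1. all serious adverse events;
2. all treatment-related adverse events;
3. all adverse events observed or reported at Area A, Area B or their donor sites, regardless of seriousness or judged cause.

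Record the location of each local event at the scheduled visits, without adding an examination. Keep the present restriction for systemic non-serious events. Summarise local events descriptively by location, and tabulate the treatment-related subset separately so that results stay consistent with the CTP001-6 analysis.

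The cost is slightly more recording at the ten follow-up visits already planned, for up to 60 patients at up to 18 sites. Reported local event counts will be higher, and the report should say that this reflects the wider rule. Because no donor-site examination is added, donor-site events will still depend on what is noticed or reported. Treatment, endpoints and sample size do not change.

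### Does the closure co-primary need rewording because it does not say whether an area first closed at Week 8 and confirmed at Week 10 counts?

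*Combined protocol and SAP*

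**What the plan says.** The Co-Primary Effectiveness Endpoints row of the Protocol Synopsis gives the endpoint as "Confirmed treatment area closure at (or prior to) the Week 8 visit". It adds that closure must be "confirmed at two consecutive study visits at least 2 weeks apart by direct visualization by a qualified clinician", and then that "Blinded Evaluator assessment of wound closure will be performed at Weeks 4, 6, 8, 10 and 12". The Design row makes the blinded reading decisive: "The blinded assessment will serve as the primary healing assessment". It also has acute healing followed through Week 12.

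The Analysis row ties an interim summary to the marketing application. On what that summary contains it says "At that time all available data will be presented", and on method, "Data will be analyzed consistent with the statistical plan develop for the CTP001-6 protocol". The same sentence says that no formal hypotheses are investigated. The Statistical Consideration row nevertheless says of the closure endpoint that "the hypothesis test of non-inferiority will be one-sided with a 5% significance level", without giving a margin. It also allows multiple imputation and pattern-mixture sensitivity analyses where data are missing.

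**The concern.** The word for confirmation and the Week 8 limit stand in one phrase, and the phrase can be parsed in two ways.

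- **Confirmed by Week 8.** Both closed visits must fall at or before Week 8, so the area must first be closed by Week 6.
- **Closed by Week 8.** The first of the two closed visits must fall at or before Week 8, and Week 10 may supply the confirmation.

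An area open at Week 6 and closed at Weeks 8 and 10 fails on the first reading and succeeds on the second. Two analysts working from the synopsis alone could therefore report different closure rates from the same data. The two arms use different mesh ratios, so equal numbers of late closures cannot be presumed, and the between-arm difference could move too. The interim adds a second worry: status is complete at Week 8 on one reading and at Week 10 on the other, while the synopsis states no cut-off date and no minimum follow-up.

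**Working it through.** There is no closure rate, margin or power figure in the synopsis to reproduce. The check is therefore on the scoring rule, with assumed inputs labelled as such.

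**1. Which areas switch.** There are 2^5 = 32 closed/open patterns over the blinded visits at Weeks 4, 6, 8, 10 and 12. Scoring all of them both ways gives 4 disagreements. All four have Week 6 open and Weeks 8 and 10 closed, with Weeks 4 and 12 either way.

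**2. Size for one arm.** Assume visits on schedule and no re-opening. Let w4, w6 and w8 be the shares first closed at each visit.

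- Closed by Week 8: rate = w4 + w6 + w8
- Confirmed by Week 8: rate = w4 + w6
- Gap = w8

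The documents do not give w8. Assumed values of 5, 10 and 15% move the rate by 5, 10 and 15 points, or 3, 6 and 9 areas per arm at the ceiling of 60 subjects.

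**3. Size for the difference.** The shift between readings is w8(ReCell) − w8(control). Take an assumed control pattern of 55/20/10/15% (Week 4 / Week 6 / Week 8 / not by Week 8). Its rate is 85% if closure by Week 8 counts and 75% if confirmation by Week 8 is required.

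| Assumed ReCell pattern | ReCell − control, closed by Week 8 | ReCell − control, confirmed by Week 8 |
|---|---|---|
| 45/20/10/25 | 75 − 85 = −10 | 65 − 75 = −10 |
| 50/20/15/15 | 85 − 85 = 0 | 70 − 75 = −5 |
| 45/20/20/15 | 85 − 85 = 0 | 65 − 75 = −10 |
| 55/20/5/20 | 80 − 85 = −5 | 75 − 75 = 0 |

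The shift can be nil or go in either direction. With no margin stated, none of these can be turned into a pass or a fail.

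**4. Interim.** Assume uniform accrual over T weeks up to the cut. A share 2/T of subjects then lies between Weeks 8 and 10. Among areas that have reached Week 8, only those open at Week 6 and closed at Week 8 are settled on one reading and pending on the other. With w8 = 10% and T = 26, that is 0.10 × 2/26 = 0.8% of areas, or 0.46 of an area per arm at 60 subjects. With T = 52 it is 0.4%. Areas seen open at Week 6 in subjects not yet at Week 8 are already failures if confirmation by Week 8 is required, and are pending otherwise: 0.25 × 2/26 = 1.9%, or 1.2 areas per arm.

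**5. What a poor interim denominator would do.** Suppose closure by Week 8 counts and someone tabulated only areas already settled, with failures declared at Week 10. On the control pattern:

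- T = 26: successes 0.55 × 20/26 + 0.20 × 18/26 + 0.10 × 16/26 = 0.623; failures 0.15 × 16/26 = 0.092; rate 0.623/0.715 = 87.1% against a true 85%.
- T = 16: successes 0.55 × 10/16 + 0.20 × 8/16 + 0.10 × 6/16 = 0.481; failures 0.15 × 6/16 = 0.056; rate 0.481/0.5375 = 89.5%.
- Pattern 30/20/20/30 with T = 26: 0.492/0.677 = 72.7% against 70%.

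The distortion is thus a few points, with no fixed ceiling. But the synopsis nowhere prescribes this denominator.

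**The case for a change.** The best case for a change is that this is a co-primary endpoint and the areas that switch are the late healers, where the wider mesh might matter. A one-sided 5% non-inferiority test is named for the endpoint despite the disclaimer about formal hypotheses, and even a descriptive rate needs a single scoring rule. One sentence would settle it, and settling it before closure data are tabulated would remove any appearance of a choice made after the fact.

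Much of this stands. The gap in the synopsis is real, and the visit schedule does not close it. Week 10 is the first scheduled visit that could confirm a Week 8 closure, which leans towards counting such areas. But blinded assessment continues to Week 12 in any case, so the lean is not proof.

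What does not stand is the step from a gap to a defect. Neither reading is unsound: each is a clear closure endpoint, applied alike to two areas on the same patient. The reviewed text is a synopsis that refers the analysis to the CTP001-6 plan, where a scoring rule for this endpoint would be expected. That plan was not available, so whether it holds the rule is unverified. A request to state a reading, with no ground for preferring one, corrects nothing that the synopsis gets wrong.

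At the interim, the imputation sentence may not have been written for subjects who have simply not reached a visit. Even so, analysts would ordinarily report such subjects as not yet evaluable rather than drop them silently or impute them.

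**Conclusion.** The concern identifies missing detail that competent analysts would fill from the CTP001-6 plan; it does not show an error in a stated rule. The readings differ by exactly the share of areas first closed at Week 8, given on-schedule visits and no re-opening. That share is unknown from the documents. The between-arm difference moves only by the gap in that share between arms, with no direction implied. At the interim, 0.8% of areas have reached Week 8 with a status that depends on the reading, under 26-week uniform accrual and a 10% Week 8 share.

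The stakes are limited because the study collects supplementary data and disclaims formal hypotheses. The absence of an interim cut-off date is a separate, minor reporting point that exists under either reading. No change to the plan is called for. The conclusion would be weaker if the CTP001-6 plan were also silent on the scoring rule.

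### Does the closure endpoint go wrong because an area that was re-treated can still count as closed?

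*Combined protocol and SAP*

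**What the plan says.** The first co-primary endpoint, in the Co-Primary Effectiveness Endpoints entry of the Protocol Synopsis, is closure at or before Week 8: "Complete wound closure is defined as skin re-epithelialization without drainage, confirmed at two consecutive study visits at least 2 weeks apart". The schedule is "Blinded Evaluator assessment of wound closure will be performed at Weeks 4, 6, 8, 10 and 12", and the Design entry adds "The blinded assessment will serve as the primary healing assessment".

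The second co-primary endpoint is the ratio of treated area to donor area, "inclusive of donor skin needed for secondary treatments", worked out for ReCell and control separately. The entry then adds: "Calculation of expansion ratios will include any donor skin required for re-treatments performed to achieve wound closure, if applicable".

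The Design entry illustrates the contrast between treatments: "if the graft plan called for a 2:1 mesh graft, for the ReCell-treated wounds, the area will be treated with 3:1 mesh graft". It also provides for standardized photographs of the treatment areas at every visit. Delayed healing (Safety) and the treating investigator's healing assessment (Other Evaluations) are likewise collected at every visit.

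The Analysis entry refers to the statistical plan of CTP001-6, which is not among the documents supplied. It promises presentation of all data available at the interim analysis and states that no formal hypotheses are being tested.

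**The concern.** Re-treatment is dealt with explicitly in one co-primary endpoint and not mentioned in the other. ReCell is applied over a more widely meshed graft than the control receives, so it is natural to ask whether the wider mesh needs repair more often. If a failed graft can be repaired and then scored as closed, the closure comparison might show no difference even though every repair fell on ReCell areas.

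Nothing else in the synopsis singles these areas out. The per-protocol definition turns on receipt of both treatments and on major deviations. The named sensitivity analyses deal with missing data, and a re-treated area that later closes is not missing. Blinded assessment starts at Week 4, so an area repaired before then has no earlier blinded record. At stake would be a closure result that flatters ReCell, in data summarized to coincide with a marketing application.

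**Working it through.** The plan states no figure to reproduce on this point. The check is of the wording, followed by arithmetic on size.

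**1. Is a re-treated area left unclassified?** The closure definition has two conditions: the wound state, and its confirmation at a second visit. Neither depends on how the area got there. The donor-skin endpoint describes re-treatment as a step taken toward closure, so closure after re-treatment is expected. The general rule therefore classifies the area without a special clause.

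**2. Which visits can establish closure?** Blinded visits are at Weeks 4, 6, 8, 10 and 12.
- If confirmation must also fall by Week 8, the qualifying pairs are 4/6 and 6/8.
- If only the earlier visit of the pair must fall by Week 8, pair 8/10 also qualifies.

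The same pairs apply to both treatments. A repaired area gets no extra time: it must be healed by Week 6, or by Week 8 on the wider reading.

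**3. How much does the scoring choice move closure?** With N pairs and an excess of d re-treated-then-closed ReCell areas over control, scoring them as not closed shifts the paired difference by d/N.
- N = 60 (the enrollment maximum): d = 1, 2, 3, 6 gives 1.67, 3.33, 5.0 and 10.0 percentage points.
- N = 30 (assumed): d = 1 gives 3.3 points.

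Any single reclassified area has this weight. The documents give no value for d.

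**4. Does re-treatment disappear from the co-primary pair?** Take one 300 cm² area per treatment (the minimum size in the Design entry) at nominal mesh ratios. Control at 2:1 uses 150 cm² of donor skin, a ratio of 300/150 = 2.00. ReCell at 3:1 uses 100 cm². With x cm² of repair skin, its ratio is 300/(100 + x):

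| x (cm²) | ReCell ratio | Control ratio |
|---|---|---|
| 0 | 3.00 | 2.00 |
| 10 | 2.73 | 2.00 |
| 25 | 2.40 | 2.00 |
| 50 | 2.00 | 2.00 |
| 100 | 1.50 | 2.00 |

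Now take 60 pairs. Assume equal areas, nominal ratios, k ReCell and no control areas re-treated in full with an m:1 graft, and every area closed in time. Without repair, the donor reduction is 1 − (1/3)/(1/2) = 1/3. A full re-treatment adds 1/m per unit area, which lowers that pair's reduction by (1/m)/(1/2) = 2/m. Hence:

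mean reduction = 1/3 − (2/m)(k/60)

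| m | k = 6 | k at zero reduction |
|---|---|---|
| 1 | 13.3% | 10 |
| 2 | 23.3% | 20 |
| 3 | 26.7% | 30 |

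For m = 2 and k = 12 the mean is 13.3%. Re-treating half of each area doubles the break-even counts to 20, 40 and 60. The closure difference is 0 for every k by assumption, while the donor-skin endpoint falls steadily. The pair of endpoints therefore registers the imbalance, in the endpoint built to carry it.

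**The case for a change.** The strongest opposing case is that neither co-primary result tells a reader how many initial grafts needed repair. In the m = 2 illustration, 19 ReCell areas and no control areas could be re-treated, with closure equal and mean donor reduction still positive (1/3 − 19/60 = 1/60, or 1.7%). The Statistical Consideration entry also describes a one-sided 5% non-inferiority test on closure, despite the Analysis entry's statement about hypotheses. If that test were used for inference, counting repaired areas as closed could narrow a difference between initial grafts.

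Some of this stands. A table of re-treatments by treatment area would help the reader, and the synopsis does not list one. But the donor skin for re-treatment must already be recorded by treatment to form the ratios, so most of that table could be derived from planned data. A repair that used no donor skin would not show there.

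The rest does not show an error. Comparing treatment strategies, repairs included, is a coherent question, and it matches a donor-skin endpoint that includes repairs. The alternative, scoring repaired areas as not closed, addresses a different question. It would make the result depend on decisions after randomization that the documents do not describe as blinded. That is a trade-off, and the alternative is not plainly better. The early gap in blinded assessment is real, but the photographs and the treating investigator's assessments still give an unblinded or uninterpreted record at each visit.

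**Conclusion.** The concern does not hold. The closure rule covers re-treated areas as written, applies equally to both treatments, and is paired with an endpoint that charges repair skin to the treatment that used it. Followed as written, the plan gives a sound comparison of the two strategies, and no figure in it needs to change.

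What remains is a reporting preference: a count of re-treatments, and a sentence or citation that makes the classification explicit. The weight per area is 1.7 percentage points of closure at 60 pairs. The total effect cannot be computed, because no re-treatment frequency or non-inferiority margin is given. The donor-skin figures rest on the assumed re-treatment mesh, extent and one-sided pattern, and serve only to show that the endpoint responds.

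The conclusion rests on the synopsis alone. The CTP001-6 statistical plan may state a rule of its own, and the synopsis's silence does not show that it lacks one. The study's role, continued access with supplementary data, also limits what depends on the point.

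### Is the donor-skin superiority test left undefined because it names a reduction in donor area while the co-primary endpoint is an expansion ratio?

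*Combined protocol and SAP*

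**What the plan says.** All of the relevant text is in the Protocol Synopsis.

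- **Co-Primary Effectiveness Endpoints**, second item, names as the endpoint "The actual expansion ratios (treatment area to donor site area, inclusive of donor skin needed for secondary treatments", with one value per arm. No between-treatment contrast is written down. The text below the item adds: "Calculation of expansion ratios will include any donor skin required for re-treatments performed to achieve wound closure, if applicable".
- **Statistical Consideration**, on testing: "for the endpoint of relative reduction in donor site area, the hypothesis test of superiority will be one-sided with a 2.5% significance level". It gives no formula, null value or test statistic.
- **Design**: the two areas are compared on healing and on "the amount of donor skin harvesting required". They must be comparable, that is "similar in burn injury depth, graft plan and size", and at least 300 cm² each. Which one receives ReCell is randomised.
- **Analysis**: "Data will be analyzed consistent with the statistical plan develop for the CTP001-6 protocol; however, there are no formal statistical hypotheses to be investigated".

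**The concern.** The endpoint section and the testing section use different names for what should be one quantity. A relative reduction in donor area can be read in two ways:

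- **Scaled:** 1 − E(control)/E(ReCell), where E is the expansion ratio.
- **Unscaled:** 1 − D(ReCell)/D(control), where D is the donor area.

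The two agree only if the paired areas are equal in size and re-treatment skin is handled alike. The Design section asks for similar sizes without a tolerance, and its own description of the comparison mentions only the amount of skin harvested.

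Two things would be at stake. An analyst could choose the metric after seeing the data. And if re-treatment skin were left out, the saving would be overstated whenever the more widely meshed ReCell areas needed more re-treatment than control. The second would be a directional error in a co-primary result that accompanies a marketing application.

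**Working it through.** The plan gives no effect size, SD or power for this endpoint, so there is no stated figure to reproduce. The check is a reading of the text followed by arithmetic on the protocol's own mesh example.

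**Step 1: which endpoint is tested.** The synopsis lists two co-primary endpoints, closure and expansion ratio. Statistical Consideration names two tests in the same order, closure and then donor area. The second test can only belong to the expansion-ratio endpoint.

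**Step 2: re-treatment skin.** The areas are measured intra-operatively: "Treatment area and donor area will be based on measurements of the treatment and donor site wound bed at the time of the grafting procedure". Taken alone, that could suggest that only the initial harvest counts. The sentence after it removes the doubt by including skin for re-treatments, and the item itself already does so. The stake is easy to show. With two 300 cm² areas at 2:1 and 3:1, donor skin is 300/2 = 150 cm² and 300/3 = 100 cm², a reduction of 1 − 100/150 = 33.3%. An assumed 50 cm² of re-treatment skin on the ReCell side makes it 1 − 150/150 = 0%. To report 33.3% in that case, an analyst would have to set aside an inclusion rule that the synopsis states twice.

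**Step 3: scaling, one subject.** Let k be the ReCell-to-control ratio of treated areas, and assume that actual expansion equals the nominal mesh ratio. The scaled reduction is 1 − 2/3 = 33.3% for any k. The unscaled reduction is 1 − k × 2/3:

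| k | Unscaled | Scaled |
|---|---|---|
| 0.8 | 46.7% | 33.3% |
| 0.9 | 40.0% | 33.3% |
| 1.0 | 33.3% | 33.3% |
| 1.1 | 26.7% | 33.3% |
| 1.2 | 20.0% | 33.3% |

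Single subjects can differ noticeably. Because allocation is random, k is as likely to lie above 1 as below, so log k averages zero and the differences largely cancel.

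**Step 4: scaling, whole trial.** Assumptions, none from the documents: SD of the log expansion contrast 0.20, and SD of log k 0.10. The latter puts 95% of area ratios between exp(−0.196) = 0.82 and exp(0.196) = 1.22, a fair rendering of similar size.

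- Variance ratio, unscaled to scaled: (0.10² + 0.20²)/0.20² = 1.25. The unscaled SD is √0.05 = 0.224.
- 95% interval: 1 − exp[−(ln 1.5 ∓ t × SD/√n)].
- n = 60: 29.8% to 36.7% scaled, 29.4% to 37.1% unscaled.
- n = 20: 26.8% to 39.3% scaled, 26.0% to 40.0% unscaled.
- Simulated type I error of the paired t test on logs at one-sided 2.5% (50,000 trials of 60 subjects): about 0.026 scaled and 0.025 to 0.026 unscaled.
- If percentages rather than logs are averaged, and k is log-normal, the mean of k is exp(0.10²/2) = 1.005. The mean unscaled reduction is then 1 − 1.005 × 2/3 = 33.0%, slightly against the device.

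**Step 5: form of the contrast.** The same 2:1 and 3:1 data are a 33.3% reduction, a ratio of 1.5 or a difference in expansion ratio of 1.0. Within a subject these share one null: the scaled reduction exceeds 0 exactly when the ratio exceeds 1 and the difference exceeds 0.

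**The case for a change.** The strongest case for a change is that one sentence would close the gap at almost no cost. The re-treatment rule is written for expansion ratios, not for a reduction, and nothing in the testing section says that one is derived from the other. The CTP001-6 plan may hold the formula, but the synopsis cites no section of it. Saying that there are no formal hypotheses does not help either, since a descriptive estimate also needs a defined quantity.

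The harm can also be made to look larger. With an SD of 0.20 for the log area ratio, the variance doubles, and at a true expansion ratio of only 1.1 the power with 60 subjects falls from about 95% scaled to 73% unscaled.

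What stands is that the formula and the cross-reference are absent from the supplied text. The larger harm does not stand. An SD of 0.20 puts 95% of area ratios between exp(−0.392) = 0.68 and exp(0.392) = 1.48, which is hard to square with the similarity requirement. At SD 0.10 the power is 90% against 95%, and a ratio of 1.1 is far from the 1.5 of the only example given. No power target is stated, and the figure of up to 60 subjects is an accrual forecast. The tension between naming a superiority test and disclaiming formal hypotheses is a separate matter and adds nothing to this one.

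**Conclusion.** No change is needed. This is a missing formula and a loose label in a synopsis, of the kind that an analyst fills sensibly from the endpoint definition or from the CTP001-6 plan. That plan is not among the supplied documents, so the fair statement is that the formula is absent here, not that it was never fixed. For the same reason, freedom to choose the metric after seeing the data is not shown.

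The one directional risk, omission of re-treatment skin, is closed by the endpoint definition. The scaling question moves the 95% limits by about half a percentage point or less with 60 subjects (29.8% to 29.4%, and 36.7% to 37.1%), and by less than one point with 20. It brings no bias on the log scale, no inflation of type I error, and no different conclusion in the 2:1 versus 3:1 example.

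This rests on paired areas that really are similar in size (log SD near 0.10), on random allocation between them, and on an assumed SD of 0.20 for the expansion contrast. The purpose of the study, continued access with supplementary data, further limits what turns on the label.
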